## PROTOCOL SUMMARY

Study Title:	A prospective, multicentre observational study to evaluate the BioMir 3D Self-Expanding Stent System in the treatment of peripheral arted disease: MIMICS-3D	
Study Objective:	The MIMICS-3D Study will evaluate safety, effectiveness and device performance within a real-world clinical population of patients undergoing femoropopliteal intervention.	
Study Device & intended	BioMimics 3D Self-Expanding Stent System.	
use	Device will be used in accordance with CE Mark approved indication and all approved and commercially available stent sizes will be included in this study.	
Study Design:	Prospective, multicentre, observational study (non-investigational)	
Device Regulatory Status:	CE Mark was approved in November 2012.	
Estimated Enrolment:	Minimum of 500 patients	
Subject Population:	Patients who receive treatment with Veryan's BioMimics 3D Stent System in accordance with the current approved CE Mark indication for use as stated in the Instructions for Use (IFU).	
Clinical Sites:	Up to 40 sites in any country where CE mark is recognised and device is legally marketed	
Study Follow-Up:	After index procedure on Day 0, patients will be evaluated at 30 days then 12, 24, and 36 months.	
Study Duration:	First patient enrolled August 2016 Last patient enrolled August 2018 Last patient, last visit August 2021	
Primary Outcome Measures:	Primary safety endpoint:The primary outcome measure for safety will be a composite of majoradverse events (MAE) comprising death, any major amputation performedon the index limb or clinically-driven target lesion revascularisation(CDTLR) through 30 days.Primary effectiveness endpoint:The primary outcome measure for effectiveness will be freedom fromclinically-driven target lesion revascularisation (CDTLR) through 12months.	
Secondary Outcome Measures:	
 
Acute technical success defined as the achievement of a final residual diameter stenosis ≤30% at the end of the procedure
 
Acute procedural success defined as both acute technical success and absence of the following adverse events: death, stroke, MI, acute onset of limb ischemia, index bypass graft or treated segment thrombosis, and/or need for urgent/emergent vascular surgery, within 72 h of the index procedure.
 
Incidence of individual components of MAE (death, any major amputation performed on the index limb or CDTLR) at 30 days, 12, 24and 36 months
 
Overall rate and incidence of adverse events from Day 0 through completion of study follow-up at Month 36.
 
Stent patency rate assessed by duplex ultrasound, as available, determined at Months 12, 24 and 36. This will be assessed using values of PSVR >2.0, >2.4; >2.5; and >3.5 each to indicate loss of patency on duplex ultrasound.
 
	

	
 
Clinical outcome: comparison of Rutherford Clinical Category measured at Baseline, Day 30, Months 12 24 and 36.
 
Functional outcome: comparison of the ankle brachial index (ABI) measurement at Baseline, within 30 days after index procedure, then at Months 12, 24 and 36.
 
Incidence of reported stent fractures through 36 months.
 
Operator assessment of device use
 

Inclusion Criteria:	
 
Patient is age ≥18 and ≤85 years at date of consent.
 
Patient has provided written informed consent for participation in the study prior to index procedure.
 
Patient has documented symptomatic peripheral arterial disease scheduled for treatment with the BioMimics 3D stent in accordance with the approved CE Mark indication and Instructions for Use (IFU)
 

Exclusion Criteria:	
 
Patients whose lesions cannot be crossed with a wire and/or balloon catheter and cannot be dilated sufficiently to allow passage of the delivery system.
 
Patients with a history of intolerance or adverse reaction to antiplatelet and/or anticoagulation therapies, bleeding diathesis, severe hypertension or renal failure.
 
Patients with known hypersensitivity to nickel-titanium.
 
Patient has a comorbidity that in the Investigator's opinion would limit life expectancy to less than 12 months.
 
Patient is pregnant or breastfeeding.
 
Patient is unable or is unwilling to comply with site standard of care procedures and follow-up visit schedules for patients undergoing femoropopliteal intervention.
 

Sponsor	Veryan Medical Limited, [name]
Principal Investigators:	[name] (Arnsberg, Germany)
Study Management:	Veryan Medical Ltd., Galway, Ireland
Monitoring:	Veryan Medical Ltd., Galway, Ireland
Data Management:	Veryan Medical Ltd., Galway, Ireland

### 1.0 INTRODUCTION AND BACKGROUND

#### 1.1 Introduction

The MIMICS-3D Study is a prospective, multicentre, observational study of the BioMimics 3D Stent System in patients undergoing endovascular intervention to relieve symptomatic peripheral arterial disease of the femoropopliteal artery. The Study is designed to enable the collection, analysis and reporting of data from "real-world" use of the BioMimics 3D Stent System used in accordance with the Instructions for Use (IFU) associated with the product's CE Mark approval.

Data collection will include that relating to safety, effectiveness and device performance and the period of observation during which data will be collected will extend from the index procedure through 3 years (36 months), according to the standard follow-up practice of the enrolling institution.

### 1.2 Literature Summary

Atherosclerosis is a chronic vascular disease that can manifest itself in the coronary, neurovascular and peripheral vascular beds with end organ and distal extremity vascular impact. Specifically, peripheral arterial disease (PAD) is a common manifestation of atherosclerosis and is a chronic occlusive arterial disease caused by plaque build-up in the arterial lumen that leads to diminished blood flow. The rising prevalence of PAD with increasing age, and within a population increasingly at risk from obesity and diabetes, is a major international health care issue with substantial economic ramifications. A recent estimate concluded that the global prevalence of PAD presently exceeds a quarter of a billion and that this number grew by more than 20% in the period 2000 to 2010^1. Patients with PAD have an increased risk of myocardial infarction, stroke, and death. Major risk factors for the development of PAD include family history, age, hypertension, cigarette smoking, diabetes, and dyslipidaemia; the greatest risk factors being diabetes and smoking. The treatment of PAD is initially directed at a combination of lifestyle or behavioural modification and medical management to hopefully slow the disease and symptom progression. When these methods fail to provide symptomatic relief, revascularisation may be achieved through endovascular or surgical approach.

### 1.3 Disease Process

Anatomically, 70% of PAD lesions are present in the femoropopliteal and tibial arteries with more than 50% of all PAD interventions involving the superficial femoral and popliteal arteries . Femoropopliteal disease is characterised by long, diffuse obstructive or occlusive lesions that create a unique slow-flow and high resistance environment.

### **1.4** Alternative Treatments / Interventions

The treatment of the femoropopliteal arteries using endovascular treatments has gained popularity with patients and physicians alike due to these procedures being less invasive, and potentially with fewer complications, than the surgical options . Percutaneous transluminal angioplasty (PTA) is one of the simplest endovascular methods to treat PAD, but the technical success and durability of this technique are often dependent on the lesion morphology .

Endovascular stenting with Nitinol stents has become an established and widely used treatment for femoropopliteal lesions, specifically the SFA and proximal popliteal arteries with reported patency rates above 80% at 12 months. However, despite improvements in stent design, restenosis is a limiting factor as a result of intimal hyperplasia following stent placement . The mechanism for the development of restenosis is multi-factorial but may include vessel injury during angioplasty, stent implantation, sub-optimal flow conditions and mechanical factors.

Given that the SFA and popliteal arteries are under continuous mobility during knee flexion the resultant mechanical forces on the vessel include compression, flexion, extension, torsion and pulsatile distension (see Figure 1). Stents deployed in these vessels are also subjected to these forces 7. The suitability of a stent for the femoropopliteal artery may therefore depend on its ability to shorten in a controlled manner, without inducing strains which lead to fatigue fracture 8. The inability of long and /or multiple straight stent segments to shorten or "take up the slack" during motion, leads to large strains, kinking and fatigue fractures . In addition, if the stent is unable to shorten, it may create biomechanical incompatibilities leading to acute and chronic injury to adjacent vessel segments subjected to substantial deformation where knee flexion may induce acute vascular angulation (kinking) 9-11. A stent which can shorten naturally in order to reduce focal deformation and provide longitudinal flexibility may therefore provide a favourable solution for recanalisation of the SFA and popliteal artery.

[figure not shown]
[figure not shown]
[figure not shown]

Figure 1: Forces on the femoropopliteal artery during lower limb movement

### 1.6 Clinical experience with BioMimics 3D Stent System

Veryan has conducted a prospective, multicentre, randomised study (Mimics study) to evaluate the safety and effectiveness of BioMimics 3D Stent System in the superficial femoral and proximal popliteal arteries (Mimics study). Data from this study was used as a basis for Veryan's application for CE Mark approval, which was approved in November 2012. The device was made available commercially in 2015.

A further study in the superficial femoral and proximal popliteal arteries (MIMICS-2 study) is currently enrolling at sites in the US, Germany and Japan to provide data for regulatory approval in the US and other countries (https://clinicaltrials.gov/ct2/show/NCT02400905). The first patient was enrolled in June 2015. It is anticipated that enrolment will be completed by August 2016, and the study will therefore be complete after 3 years' follow-up in 2019.

### 1.7 BioMimics 3D Study Purpose

The BioMimics 3D Study is designed to enable the collection, analysis, reporting and presentation of data from use of the BioMimics 3D Stent System purchased by the hospital or clinic and used in accordance with the Instructions for Use associated with the product's CE Mark approval. The intent of this post-market observational study is to increase the understanding of the performance of the BioMimics 3D Stent System in a larger population of patients representative of a real-world situation. In addition, a broader cohort of interventionalists (i.e., angiologists, cardiologists, radiologists and vascular surgeons) will be included than that so far involved in Veryan's clinical evaluation.

There is an extensive body of literature supporting femoropopliteal stenting including in 'real-world' registries  The principles of evaluating safety at 30 days and effectiveness (patency of the stented segment) at 12 months are well-established clinical endpoints for such a real-world registry. However, the specific attributes of the BioMimics 3D stent (promotion of swirling blood flow and improved biomechanical compatibility within the femoropopliteal artery) have the potential for chronic outcome benefits supporting the longer term follow-up objective of this study.

### 2.0 STUDY DEVICE

### 2.1 Intended Use

The BioMimics 3D Self-Expanding Stent System will be used in accordance with the current approved CE Mark indication for use as stated in the Instructions for Use (IFU).

The current IFU is included in Appendix A.

### 2.2 CE Mark Status

CE Mark was approved in November 2012.

### 2.3 Device Preparation and Deployment Procedure

The BioMimics 3D Stent will be prepared and deployed as described in the IFU that accompanies each device.

Procedures for patient preparation and follow-up, including medication and vascular access, will be according to hospital / institutional standard of care.

#### 2.4 BioMimics 3D stent and delivery system size matrix

All CE Mark approved and commercially available stent sizes will be included in this study. The current size matrix can be found in the IFU.

### 3.0 STUDY PLAN

#### 3.1 Study Objective

The MIMICS-3D Study will evaluate safety, effectiveness and device performance within a real-world clinical population of patients undergoing femoropopliteal intervention.

### 3.2 Design

Prospective, multicentre, observational study (non-investigational) of patients who receive treatment with Veryan's BioMimics 3D Stent System.

#### 3.3 Enrolment

A minimum of 500 patients will be enrolled in the study. The study will be conducted at up to 40 centres in any country where CE Mark is recognised and the device is legally marketed.

A minimum of 50 patients treated with drug coated balloon (DCB) will be enrolled (DCB cohort). All primary and secondary endpoints will be assessed separately for this cohort.

#### 3.4 Study Duration and Follow-Up

It is anticipated that enrolment will commence in August 2016 and is expected to continue until August 2018. The last patient visit is expected in 2021.

Patient follow up will be in accordance with standard of care. Data will be collected according to the following schedule: baseline (medical history), index procedure through discharge, 30 days ( $\pm$  7 days), 12 months (365 days  $\pm$  60 days), 24 months (730 days  $\pm$  60 days) and 36 months (1095 days  $\pm$  60 days). Follow-up may be conducted by clinic visit or telephone, according to site standard of care.

### 4.0 ENDPOINTS AND SUBJECT POPULATION

#### 4.1 **Primary Outcome Measures**

#### 4.1.1 **Primary safety endpoint:**

The primary outcome measure for safety will be a composite of major adverse events (MAE) comprising death, any major amputation performed on the index limb or clinically-driven target lesion revascularization (CDTLR) through 30 days.

### 4.1.2 **Primary effectiveness endpoint:**

The primary outcome measure for effectiveness will be freedom from clinically-driven target lesion revascularization (CDTLR) through 12 months.

### 4.2 Secondary Outcome Measures

• Acute technical success defined as the achievement of a final residual diameter stenosis <30% at the end of the procedure

- Acute procedural success defined as both acute technical success and absence of the following adverse events: death, stroke, MI, acute onset of limb ischemia, index bypass graft or treated segment thrombosis, and/or need for urgent/emergent vascular surgery, within 72 h of the index procedure.
- Incidence of individual components of MAE (death, any major amputation performed on the index limb or CDTLR) at 30 days, 12, 24 and 36 months
- Overall rate and incidence of adverse events from Day 0 through completion of study follow-up at Month 36.
- Stent patency rate assessed by duplex ultrasound, as available, determined at Months 12, 24 and 36. This will be assessed using values of PSVR >2.0, >2.4; >2.5; and >3.5 each to indicate loss of patency on duplex ultrasound.
- Clinical outcome: comparison of Rutherford Clinical Category measured at Baseline, Day 30, Months 12 24 and 36.
- Functional outcome: comparison of the ankle brachial index (ABI) measurement at Baseline, within 30 days after index procedure, then at Months 12, 24 and 36.
- Incidence of reported stent fractures through 36 months.
- Operator assessment of device use

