### 7.0 ADVERSE EVENTS

For the purpose of this Study all potentially device-related and procedure-related adverse events, major adverse events, and all vascular adverse events in the target limb will be documented throughout the 36-month visit and reported to Sponsor via the eCRF.

The Sponsor shall review all adverse events for their relationship to the Study device(s) and/or procedures and comparative anticipated safety event rates. The Sponsor will conduct evaluations of any device-related event per standard operating procedures.

An independent Clinical Events Committee (CEC) will be responsible for systematic review and adjudication of all Major Adverse Events including death, and all potentially device- -related adverse events.

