### 7.1 Adverse Event definitions

Adverse event (AE) is any untoward medical occurrence, unintended disease or injury, or untoward clinical signs in subjects, whether or not related to the investigational device or procedure. In addition, the definition of AE applies to any event with an onset during enrolment / index procedure or to any underlying diseases, present at baseline, that exacerbate in severity post study procedure. Therefore, an underlying disease that was present at the time of enrolment is not reported as an AE, but any increase in the severity of the underlying disease is to be reported as an AE. This definition includes events occurring during the follow-up period.

Adverse Device Effect (ADE) / Device-Related Adverse Event: an adverse device effect (or devicerelated adverse event) is defined as any untoward adverse effect when, in the judgment of the Investigator, the clinical event has a reasonable time sequence associated with use of the investigational device and is unlikely to be attributed to concurrent disease or other procedures or medications. It is reasonable to believe that the device directly caused or contributed to the adverse event.

NOTE 1: This definition includes adverse events resulting from insufficient or inadequate Instructions for Use, deployment, implantation, installation, or operation, or any malfunction of the investigational medical device.

NOTE 2: This definition includes any event resulting from user error or from intentional misuse of the investigational medical device.

**Procedure-Related Adverse Event**: an adverse event is considered to be procedure-related when, in the judgment of the Investigator, it is reasonable to believe that the event is associated with the assigned study procedure and is not specific to the Study device (i.e., BioMimics 3D Stent System) used. Other products, surgical techniques, or medications required specifically for the procedure are likely to have contributed to the occurrence of the event.

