#### 7.2 Adverse Event Reporting Requirements

#### 7.2.1 General Reporting Requirements

The following adverse events should be recorded on the eCRF through 36 months post-index procedure:

- All potentially device and/or procedure-related adverse events
- All major adverse events (MAE)
- All vascular adverse events in the target limb.

The report should include: description of event, severity, duration, action taken, treatment outcome and relationship of the adverse experience to the study device and/or procedure (i.e., unrelated, possibly related, related or relationship not assessable).

The following definitions for rating severity of adverse events will be used:

Mild: Awareness of signs or symptoms, but easily tolerated; are of minor irritant type; causing no loss of time from normal activities; symptoms would not require medication or a medical evaluation; signs or symptoms are transient.

Moderate: Interferes with the subject's usual activity and/or requires symptomatic treatment.

Severe: Symptom(s) causing severe discomfort and significant impact of the subject's usual activity and requires treatment.

All reportable events should be followed until resolution or the end of the study.

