**Limb Ischemia**: Deficient supply of oxygenated blood to the tissues in the limbs that is due to obstruction of the inflow of arterial blood characterised by pain and/or discoloration of the limb and/or tissue loss.

Luminal Patency: Restenosis <50% as determined by angiography or duplex ultrasound.

**Major Adverse Event (MAE):** An MAE comprises all-cause death, any major amputation performed on the target limb or clinically-driven target lesion revascularisation.

**Myocardial Infarction (MI)**: Evidence of myocardial necrosis in a clinical setting consistent with myocardial ischemia.

**Patency, Primary Stent:** Patency is defined as the composite of (1) freedom from more than 50% restenosis within the stented segment and (2) freedom from clinically-driven target lesion revascularisation (TLR).

**Patency, Tibioperoneal Run-Off:** Subject has at least one patent tibioperoneal run-off vessel with <50% stenosis confirmed by angiography.

Perforation: Puncture of an arterial wall.

**Pseudoaneurysm**: Disruption of the arterial wall characterised by an out-pouching or pocket with swirling, flowing blood outside of the confines of the arterial lumen.

Recurrent Occlusion: Occlusion (i.e. total obstruction of vessel lumen) after a successful canalisation.

**Recurrent Thrombosis**: Thrombosis (i.e. sub-total obstruction of vessel lumen) following successful treatment.

**Reference Vessel Diameter, Proximal (RVD**prox): Diameter of normal vessel immediately proximal to the treated segment.

Reference Vessel Diameter, Distal (RVDdist): Diameter of normal vessel immediately distal to the treated segment.

**Renal Failure (Acute):** Acute post-operative renal insufficiency resulting in one or more of the following: (a) increase of > 1.0 mg/dl in serum creatinine from most recent prior measured level, and current measured absolute value is > 2.0 mg/dl; (b) a new requirement for dialysis.

**Renal Insufficiency**: An increase in serum creatinine of  $\geq$  1.0 mg/dl over previous value requiring medical treatment but which does not require dialysis to resolve.

**Respiratory Failure:** New onset of respiratory insufficiency that requires placement of endotracheal tube and/or pneumothorax with or without chest tube.

**Respiratory Insufficiency:** Deterioration of subject's respiratory efforts that require supportive or medical treatment.

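### The secondary endpoint called the overall adverse event rate is wider than what section 7 records, and capture of a 72-hour stroke or MI for procedural success rests on a relatedness judgement

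*Combined protocol and SAP*

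**What the plan says.** Section 4.2, repeated in the protocol summary, lists among the secondary outcomes the "Overall rate and incidence of adverse events from Day 0 through completion of study follow-up at Month 36". Section 7.1 defines an AE as any untoward occurrence "whether or not related to the investigational device or procedure".

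The recording rule is narrower. Section 7.0 says that, for this study, "all potentially device-related and procedure-related adverse events, major adverse events, and all vascular adverse events in the target limb will be documented". Section 7.2.1 repeats the limit as a list, introduced by "The following adverse events should be recorded on the eCRF through 36 months post-index procedure". Its first item is "All potentially device and/or procedure-related adverse events"; the other two are MAE and vascular AEs in the target limb. Section 12.0 defines the middle class: "An MAE comprises all-cause death, any major amputation performed on the target limb or clinically-driven target lesion revascularisation". Stroke and MI are not in it.

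A second outcome in section 4.2, acute procedural success, requires technical success together with "absence of the following adverse events: death, stroke, MI, acute onset of limb ischemia, index bypass graft or treated segment thrombosis" and no urgent vascular surgery, all within 72 hours. No relatedness condition is attached to the stroke and MI components.

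Sections 6.3 and 6.4 and Table 1 list adverse events as a data item with no filter. Nothing in section 9 redefines the AE endpoint; section 9.4 simply tabulates all secondary endpoints.

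**The concern.** An endpoint named overall should count every event that meets the protocol's own AE definition. If sites follow section 7, a whole group of such events is never required on the eCRF, and no analysis can bring them back. Section 9.8 allows interim results to be presented or published, and section 11.4 allows the sponsor to use results for marketing. In those settings the word overall would be taken literally.

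For procedural success the worry is narrower. One component of a success definition is captured only through the site's own judgement that the event may be related. Section 1.2 notes that patients with peripheral arterial disease already carry a raised risk of MI and stroke, so attributing an early event to the underlying disease is plausible. Any event lost this way turns a failure into a success.

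**Working it through.** The plan gives no figure for either endpoint. The interval widths in section 9.6 concern the primary endpoints only. They reproduce: with n = 500 the exact interval is 5.46 points wide at 90% and 1.99 at 99% (stated: 5.5 and 2), and with n = 450 the width at 75% is 2 × 1.96 × √(0.75 × 0.25 / 450) = 8.00 points (stated: about 8). They have no bearing on what follows.

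**1. Endpoint against recording rule.**

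| Event | AE under 7.1, so within the 4.2 endpoint | Recording required by 7.0 and 7.2.1 |
|---|---|---|
| Death, any cause | yes | yes (MAE) |
| Vascular event in the target limb | yes | yes |
| Non-fatal event elsewhere, judged potentially related | yes | yes |
| Non-fatal event elsewhere, judged unrelated | yes | no |

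The last row is the gap.

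**2. Other text on scope.** The unfiltered items in 6.3, 6.4 and Table 1 can be read as asking for all AEs, or as headings whose content section 7 defines. Section 7.2.2 and Table 2 join serious to potentially related in one phrase. It is unclear whether unrelated serious events are meant. With up to 40 sites, different readings would mix two or more definitions in one rate.

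**3. Illustration for the AE rate.** All rates here are assumptions. Let T be the true share of patients with any AE, and s the share of those patients whose only events are unrecorded. The recorded incidence is T(1 − s), and the shortfall is T × s, in percentage points:

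| T | s = 10% | s = 25% | s = 50% |
|---|---|---|---|
| 40% | 4 | 10 | 20 |
| 60% | 6 | 15 | 30 |
| 80% | 8 | 20 | 40 |

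With n = 500, a 95% Agresti-Coull interval around the recorded rate contains the true rate only in the first cell (recorded 36.0%, interval 31.9% to 40.3%, truth 40%). In the other eight it does not; for example, T = 60% and s = 10% gives 54.0%, with interval 49.6% to 58.3%. These figures are for patient-level incidence. A patient with one recorded and one unrecorded event still counts, so a share of events cannot be carried over to a share of patients.

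**4. Procedural success.** Limb ischaemia and thrombosis in the treated limb are target-limb vascular events, and Table 1 records target-limb interventions from Day 0. Deaths are MAE. What remains is a non-fatal stroke or MI. I looked for a backstop:

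- Section 6.3 runs only to discharge, and no section ties discharge to 72 hours.
- The next scheduled contact is Day 30, which may be by telephone (3.4, 6.1).
- Adjudication by the Clinical Events Committee is required only for MAE and potentially device-related events (7.0, 10.15).

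Let r be the share of patients whose only failing component is a non-fatal stroke or MI within 72 hours, and u the share of those judged unrelated and not recorded. The overstatement is r × u. With r from 0.5% to 2% and u from 0 to 50% (both assumed), it runs from 0 to 2% × 50% = 1.0 point, or 500 × 0.02 × 0.5 = 5 patients. With u = 100% it is 0.5 to 2.0 points.

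**5. Aborted procedures.** Section 5.3 collects only device failures and malfunctions and device-related AEs for these patients. They fall outside the modified intention-to-treat set that section 9.4 uses for secondary endpoints, so they do not change the calculation above.

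**The case against.** A reader might infer that only related events are recorded, that every unrelated systemic event is lost, and that both results therefore come out too favourable. The documents do not support that reading.

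- The threshold is potentially related, to device or procedure, and the scale in 7.2.1 includes possibly related and not assessable. Section 8.1 lists both MI and stroke as complications. Most such events within 72 hours of an arterial procedure would probably be recorded.
- Unrelated deaths are captured, because the MAE definition covers all-cause death.
- Section 6.3 asks for adverse events through discharge without a filter, which may cover some or all of the 72 hours.
- The eCRF is not in the documents and may already ask about early stroke and MI.

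These points stand. They reduce the procedural-success issue to a possible and probably small bias.

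It can also be said that restricted AE collection is a legitimate choice in a descriptive, standard-of-care study, that section 7.0 states the scope openly, and that unrelated events say little about device safety. That is fair as a defence of the collection rule. It does not defend the endpoint's name, which promises something that the rule does not deliver. Nor do the unfiltered items in section 6 rescue it: if they override section 7, the list in 7.2.1 has no function, and if they do not, the endpoint is misnamed.

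**Conclusion.** Wrong as written, for secondary endpoints only. If section 7 is followed, a rate labelled overall omits non-fatal, unrelated events outside the target limb and is understated. The documents give no basis for the amount; the 4 to 40 points shown above only translate the assumed values of T and s. If sites differ in which section they follow, the rate has no single definition.

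For acute procedural success, overstatement is possible but not certain. It needs a non-fatal stroke or MI within 72 hours, as the only failing component, that the site judges not even potentially related and leaves off the eCRF. Under the assumed rates the effect is 0 to 1 point, and 2 points if every such event is missed.

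The primary endpoints are unaffected: all their components are MAE, recorded regardless of relatedness and adjudicated.

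**What to change.** 1. In section 4.2 and the summary, rename the endpoint *rate and incidence of reportable adverse events (potentially device- and/or procedure-related, MAE, target-limb vascular)*. Bring 6.3, 6.4, Table 1, 7.0, 7.2.1, 7.2.2 and Table 2 into line with it, including whether unrelated serious events are within the expedited wording.
2. Add to 7.0 and 7.2.1 that any stroke or MI within 72 hours of the index procedure is recorded irrespective of relatedness. State whether these events also count in the renamed endpoint.

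The cost is a text amendment and, unless the eCRF already asks, an item on stroke and MI within 72 hours. No test beyond standard of care is needed. The downside is a few more reported events and possibly a slightly lower success rate. Widening collection to all AEs would also remove the mismatch, but at a much larger burden on sites; renaming is enough.
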